3.4. Study population

Pre-PDC Phase One:

All infants discharged from the Rwinkwavu District Hospital neonatal unit during the designated time period fulfilling the inclusion criteria: children were included if they were discharged between October 2011-October 2013 (prior to PDC implementation).

Post-PDC Phase Two:

All children enrolled in the PDC are eligible. PDC serves children up to age five years with prematurity, low birth weight, birth asphyxia, other perinatal risks, and other developmental delays.

Expanding-PDC Phase Three:

All children and their caregivers enrolled in the PDC clinics in S. Kayonza and Kirehe Districts are eligible. PDC serves children up to age five years with prematurity, low birth weight, birth asphyxia, other perinatal risks such as post CNS infections_cerebral malaria and meningitis, and other developmental delays.

3.5. Selection of study population

3.5.1. Inclusion criteria

Baseline Phase One:

All infants discharged from Rwinkwavu hospital neonatal unit and born at less than 37 weeks and infants born less than 2 kilograms during the designated study period.

Post-PDC Phase Two:

All children under five years of age enrolled in PDC in Rwinkwavu District Hospital catchment area PDC clinics, will be included in Aim 3 and Aim 4b. Aim 4a will include only preterm and/or LBW (<2000g) infants for comparison with the baseline population of similar infants.

Expanding-PDC Phase Three:

All children under five years of age and their caregivers referred to or enrolled in PDC in Rwinkwavu and Kirehe District Hospital catchment areas. In addition, newborns and their caregivers from Rwinkwavu and Kirehe District Hospital catchment areas will be included as the primary referral patient population to PDC. PDC providers will also be included in some components of the evaluation.

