3.2. Study design

Pre-PDC Phase One:

The first phase is a **cross-sectional study** of infants discharged from a district hospital unit using caregiver report of medical and developmental outcomes as well as relying on measured growth parameters for nutritional status. This study will serve as a baseline of developmental, medical, and nutritional outcomes for comparison to similar children who received services from the PDC.

Post-PDC Phase Two:

All under 5 years of age, high risk (preterm, LBW) children enrolled in PDC since April, 2014 when PDC was initiated. The second phase will be a second cross-section of children who have been receiving services from the PDC from April 2014 when the clinic launched until present. The study will describe PDC implementation, demographic characteristics, and clinical, nutritional and developmental outcomes of all children from zero to five years of age enrolled in PDC from April 2014 to the time of study.

Post-PDC Phase Three:

This phase will use mixed methods, with data sources including routinely collected data, chart review, household data collection, focus groups and interviews to evaluate the PDC as it expands to new areas. The study will provide essential information of the feasibility of the PDC model at larger scale. The study will describe barriers to care, retention, long-term patient outcomes, and provider and patient experiences, quality of care delivered in the PDC especially on growth monitoring and developmental screening and costing of the PDC.

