3.5.2. Exclusion and Stop Criteria

Pre-PDC Phase One:

1. Any infant whose family is unwilling to consent to study or decides to stop the home visit at any time.
2. Congenital heart disease per neonatal register
3. Genetic dysmorphology per neonatal register
4. Birth asphyxia per neonatal register

Post-PDC Phase Two:

1. For Aim 4a, exclusion criteria will match the Baseline Phase One exclusion criteria listed above.

Expanding-PDC Phase Three:

1. Children who do not meet inclusion criteria will be excluded.

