3.5.5. Proposed Intervention

Children in Phases Two and Three of this study have participated in the PDC program as described previously, unless they are in a comparison group. The PDC provides medical, nutritional and developmental supportive programs to at-risk children under age five using trained nurses and social workers in addition to overall clinic supervision by a general practitioner. Children are referred to the PDC from the hospital (neonatal unit, maternity, inpatient pediatrics, and the outpatient or emergency departments), health centers, and from the community. Children are eligible to enroll in the PDC if they meet the following program eligibility criteria: prematurity, low birth weight (<2000grams), hypoxic ischemic encephalopathy, hydrocephalus, cleft lip and palate, trisomy 21, post central nervous system infections (meningitis and cerebral malaria) severely malnourished children requiring hospitalization post-discharge, as well as children presenting with other developmental delays. Children come in for routine visits, on a timeline determined by their specific condition. On each PDC clinic day, social workers facilitate a group counseling session focused on topics relevant to children's growth and development. After group sessions, children undergo a clinical screening and growth monitoring by a nurse as well as one-on-one sessions with a social worker to identify needs for additional social support whether financial, emotional, nutritional, or a home visit. PDC social support groups are formed to engage father's in the care of their children. Health

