We will use bivariate analyses to compare the outcomes of infants who received PDC services with a random sample of children from rural communities in Rwanda (a pre-existing dataset). Developmental delay will be scored as a binary outcome looking at the proportion of children who failed one or more ASQ-3 domain in the random sample of Rwandan children from rural areas to the proportion of children enrolled in PDC who failed one or more ASQ-3 domain. We will use a chi square test or fishers exact test look for significant differences in the number of children with developmental delay between children who received PDC services and those who did not. We will use chi squared or fishers exact test to assess for differences in nutritional (normal, moderate, and severe malnutrition indicators) among the two groups. Medical outcomes will not be assessed because the comparison database only collected data on demographics and current

developmental and nutritional status.

Expanding-PDC Phase Three:

Aim 5: Analyses of PDC expansion will be focused on descriptive analyses of process, output and selected outcome measures including, patient outcomes, quality of care, and quality improvement interventions according to defined standards, training and mentorship activities, referral rate, retention, barriers and facilitators to care, patient and provider experiences, and patient health, nutritional, and developmental outcomes. These data will be used to monitor impact of PDC on patient outcomes as well as continuous quality improvement of the model, such as the introduction of the new mHealth application to improve quality of growth monitoring. As appropriate, bivariate and multivariate analyses will be used. Qualitative analysis will use thematic coding.

Aim 5. 1. Descriptive analyses to evaluate the implementation of interventions to promote breastfeeding from as early as day one of life among newborns in the referring hospital neonatal units will focus on analysis of exclusive breastfeeding rates and proportion of newborns requiring formula pre-post quality improvement interventions.

4. Study Limitations

Pre-PDC Phase One:

1. Data is based on caregiver report and therefore subject to recall bias of the caretakers.

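### Aim 4b pools children enrolled because of delay or severe malnutrition with all other PDC children and compares them crudely with a rural sample on those outcomes; Aim 4a has no 36-month age ceiling on the PDC side

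*Combined protocol and SAP*

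**What the plan says.** **Aim 4b population.** Section 3.5.1 of the combined protocol and SAP says that all children under five "enrolled in PDC in Rwinkwavu District Hospital catchment area PDC clinics, will be included in Aim 3 and Aim 4b"; only Aim 4a is limited to preterm or low-birth-weight (LBW) children. Section 3.4 describes the source group: "PDC serves children up to age five years with prematurity, low birth weight, birth asphyxia, other perinatal risks, and other developmental delays". The entry criteria in section 3.5.5 end with "severely malnourished children requiring hospitalization post-discharge, as well as children presenting with other developmental delays". On exclusions, section 3.5.2 gives a Phase Two rule for one comparison only: "For Aim 4a, exclusion criteria will match the Baseline Phase One exclusion criteria listed above".

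**Aim 4b analysis.** Section 3.6.2 makes ASQ-3 developmental delay and undernutrition the main Aim 4 outcomes. Section 3.6.4 plans bivariate chi-square or Fisher tests against a random sample from rural communities, looking for "differences in the number of children with developmental delay between children who received PDC services and those who did not". Medical outcomes are left out because "the comparison database only collected data on demographics and current" developmental and nutritional status.

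**Ages.** Sections 2, 3.1 and 3.6.2 place the Phase One children at 12-36 months when assessed. For the PDC side, sections 3.5.3 and 3.6.1 require at least 12 months' enrolment before the household interview; no section gives an upper age below five years. For Aim 4b, sections 2, 3.6.2 and 4 already restrict the comparison to the same or similar ages.

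**The concern.** In Aim 4b some children are in the PDC group because they already had the condition that is later counted as the outcome, whereas the comparison group was sampled at random. A higher PDC prevalence could then come from the referral route, from the raised risk of preterm and LBW infants that the Background describes, or from how children fare under the programme. One pooled proportion cannot separate these. The selection acts against the PDC group, so it could produce an apparent deficit or hide a real advantage among children enrolled for other reasons.

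In Aim 4a, PDC children older than 36 months would have no baseline counterparts of the same age, and age would be mixed with PDC exposure.

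**Working it through.** The plan gives no sample size, expected prevalence or effect size for Aim 4a or 4b, so there is no figure to reproduce. The check is a reading of the sections, followed by an illustration on assumed inputs.

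**1. Does any section split or adjust Aim 4b?**
- Section 3.6.2 plans malnutrition by age category or medical condition, but under Aim 3, with no rural comparator.
- Section 3.6.4 plans logistic regression if power allows, but under Aim 4a.
- Section 3.6.4 allows multivariate analyses as appropriate, but under Aim 5.
- Section 3.5.2 applies exclusions to Aim 4a only.
- Section 4 disclaims causality because the study is cross-sectional; it does not mention entry on the outcome.

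None reaches Aim 4b.

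**2. How large could the effect be?** All inputs here are assumptions:
- p = delay prevalence in the rural sample, and equally in PDC children enrolled for other reasons: 0.20-0.40
- q = delay prevalence at assessment in children enrolled for delay: 0.70-0.90
- f = their share of the PDC group: 5%-30%

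Expected pooled PDC prevalence: m = (1 − f)p + fq. Crude odds ratio: [m/(1 − m)] / [p/(1 − p)].

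With p = 0.30 and q = 0.90:

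| f | m | Odds ratio |
|---|---|---|
| 5% | 0.285 + 0.045 = 0.33 | 1.15 |
| 10% | 0.27 + 0.09 = 0.36 | 1.31 |
| 20% | 0.24 + 0.18 = 0.42 | 1.69 |
| 30% | 0.21 + 0.27 = 0.48 | 2.15 |

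Over the whole assumed grid the odds ratio runs from 1.06 (p = 0.40, q = 0.70, f = 5%) to 2.78 (p = 0.20, q = 0.90, f = 30%). In children not enrolled for delay the expected odds ratio is 1.0 by construction.

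At p = 0.30, q = 0.90 and f = 20%, a two-sided 5% test with n per group would be significant against the PDC group with probability 0.42, 0.71 and 0.94 at n = 100, 200 and 400 (also assumed).

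**3. Could a real advantage be hidden?** If other PDC children have prevalence t below p, the pooled difference is zero at f = (p − t)/(q − t). A 10-point advantage is fully masked at shares from 0.10/0.80 = 12.5% (p = 0.20, q = 0.90) to 0.10/0.40 = 25% (p = 0.40, q = 0.70).

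**4. Aim 4a age.** At least 12 months' enrolment implies an age of at least about 12 months at interview. None of the Phase One exclusions (refusal or stopping of the visit, congenital heart disease, dysmorphology, birth asphyxia) concerns age. A child who enrolled after 24 months of age would be past 24 + 12 = 36 months at interview.

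If a share g of the PDC group lies outside 12-36 months and its prevalence differs by d (both assumed), the crude difference shifts by g × d. With d of 10-20 points, that is 1-2 points at g = 10% and 5-10 points at g = 50%.

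**The case against.** The best defence is that Aim 4b is descriptive. Sections 2 and 3.6.2 set out to describe PDC children in comparison with the general population, and section 4 disclaims causality. A reader might infer from "differences in the number of children with developmental delay between children who received PDC services and those who did not" that the plan claims a programme effect. The documents do not support that: the phrase repeats the Aim 4a sentence and names group membership, and the paragraph opens by identifying the comparator as a random rural sample. Describing the PDC population this way is legitimate. What remains is that the pooled figure does not show which entry groups drive it, and no caveat tells readers about the selection.

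Second, the outcome is not measured at entry. Household data come at least 12 months later, after services, and severe malnutrition may have resolved. This stands: the selection is on an earlier value, and it biases the comparison only as far as status persists.

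Third, the Aim 3 tabulation of malnutrition by condition covers the same children. It helps for nutrition, but it gives no contrast with the rural sample.

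On Aim 4a, a reader might infer that many PDC children are too old. That is not shown. The PDC opened in April 2014; a child enrolled at birth then would be about 25 months old in May 2016, where the Phase Two timeline ends, and about 41 months at the September 2017 approval. ASQ forms are age-specific and growth is expressed in z-scores, which reduces confounding by age without removing it.

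Two further readings also fail. Aim 4b does not ignore age; its restriction is stated, and repeating it in section 3.6.4 would be editorial. Section 3.2 describes Phase Two both as "All under 5 years of age, high risk (preterm, LBW) children enrolled in PDC since April, 2014 when PDC was initiated" and as "all children from zero to five years of age enrolled in PDC from April 2014 to the time of study", but section 3.5.1 settles the population aim by aim, so that is a wording matter.

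**Conclusion.** The point holds and should be fixed. Aim 4b compares a group partly selected on earlier delay or severe malnutrition with a random sample on those outcomes, without a split by reason for enrolment and without a stated caveat. The direction is against the PDC group. The size cannot be determined: the odds ratios of 1.06 to 2.78 rest wholly on assumed prevalences and shares and are not estimates for this study. A reader might take the preterm/LBW stratum as a clean measure of benefit; it is not, because the Background says these infants already carry raised risk relative to the general population.

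The Aim 4a gap is secondary. A ceiling matching the baseline is missing, and the number of PDC children above 36 months is unknown, so confounding by age is possible but not demonstrated.

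**What to change.** - **Section 3.6.4, Aim 4b.** Keep all PDC children, but report delay and undernutrition against the age-matched rural sample by recorded reason for enrolment: preterm/LBW, developmental delay, severe malnutrition (where recorded) and other conditions. State that the pooled contrast describes the PDC population, and that neither it nor the preterm/LBW stratum is a programme effect.
- **Sections 3.5.1 and 3.6.4, Aim 4a.** Restrict the PDC group to children aged 12-36 months at assessment.

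The cost is text changes and extra tables. Section 3.5.3 already names enrolment forms and the electronic record as sources, so no new collection is needed. The documents do not show that severe malnutrition is recorded as an entry reason, so that stratum may be incomplete. Strata will be smaller and intervals wider, and the age limit may remove some Aim 4a children.

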3.1. Study description

This study has three phases. In the first phase, descriptive study will investigate at the community level the developmental, medical and nutritional outcomes of infants discharged from the neonatal unit, aged between 12 to 36 months at the time of data collection. In the second phase, the study will assess the services provided to children enrolled in the PDC and compare their outcomes to children from the first phase as well as to an existing random sample of children from an existing database. In the third phase, research will focus on answering questions raised from the initial PDC study aims – including patient and provider experiences, expansion of the PDC model, overall clinic processes, enrolment rates and retention, cost-effectiveness, and longer term outcomes of children enrolled in the PDC to further help refine the PDC model and maximize benefits for children.

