3.5.3 Sampling

Pre-PDC Phase One:

Potential participants will be identified and sampling will be conducted in the following manner. The study coordinator will use the Rwinkwavu neonatal registry after obtaining consent from the medical director to identify potential study participants based on the inclusion criteria outlined above. The following identifiers will be extracted from the registry: name, sex, date of birth, discharge date and mother's name. After the identification of potential participants, the patient files will be located and examined to compile the demographic information of the infants: sector, cell, village, and health center.

Post-PDC Phase Two:

All children enrolled in the PDC are eligible and no new data will be collected for Aim 3. Children will be identified through PDC patient records, which include patient registers, patient enrollment forms, routine program forms, and the electronic medical record (EMR). To complete Aim 4, additional assessments of children's growth, development, and home environment including parenting practices will be conducted through household interviews with the primary

caregivers of PDC patients. Patient names and household location will be extracted from the EMR of patients who enrolled in the PDC at least 12 months prior to data collection.

Expanding-PDC Phase Three:

All children enrolled in the neonatal units or PDC, their caregivers, and PDC providers are eligible for participation in this aim. Children will be identified through neonatal unit and PDC patient records, which include patient registers/charts, patient enrollment forms, routine program forms, and the electronic medical record (EMR).

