Patient flow: Group education, individual social worker screening, clinical evaluation including danger sign assessment, nutritional assessment/classification/treatment, developmental screening/therapy, and condition-specific screening and treatment.

Aim 4: Compare developmental, medical, and nutritional outcomes of children who were enrolled in the PDC to other children on the main outcomes of prevalence of developmental delay as measured using the Ages and Stages Questionnaires (ASQ-3) and the prevalence of undernutrition (stunting, wasting, underweight) using anthropometric assessments.

This aim is to describe the clinical, nutritional, and developmental outcomes of vulnerable patients enrolled in PDC in comparison with:

- a. Medically vulnerable infants who did not receive PDC support. This comparison will be made using a cohort of preterm/LBW children who were born in Rwinkwavu District Hospital (RDH) before PDC started with medical, nutritional and developmental outcomes assessed at 12-36 months of age (the dataset from Aim 1).
- b. The general population of rural Rwandan children.² This comparison will be looking at developmental outcomes of children followed in PDC compared to the similar age children from the general population using UNICEF data that was collected in children ages 0-11 months and 24-35 months randomly sampled from ten rural sectors of the country.

Additional variables to be measured include (See Appendix F for data source forms of routinely collected data and Appendix A for household interview forms. All measures used in the household interview were previously used in the two comparison datasets):

- Descriptive characteristics of caregivers.
- Proportion of visits where a nutritional screening was done, danger sign screening was done, and patient had a documented ASQ within the 6 months prior to visit date.

² This existing data set was collected by UNICEF, Harvard School of Public Health, Partners In Health, and the University of Rwanda. [name] and [name] were investigators on both study teams and have access to the data.

- Proportion of children who received nutrition supplement.
- Proportion of currently enrolled children with a visit in the reference quarter whose caregivers have had at least one documented ECD counseling session
- Proportion of children with moderate or severe chronic malnutrition (height/age Z score < 2 or height/age z score < 3) at the last visit.

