2. The high-risk infants who were hospitalized in the neonatal unit were not from one specific sector. The Rwinkwavu Neonatal unit serves as a referral center for the Southern Kayonza district. Each of the sectors within the district may not be environmentally identical. Specifically the availability of food, amount of rain and distance to health centers are factors that could influence the outcomes of the high-risk neonates and therefore could result in residual confounding.
3. The gestational age and birth weight are subject to misclassification.
4. This is cross sectional data, and therefore any associations found are unable to assess causality.
5. Exclusion criteria undiagnosed by register are subject to misclassification.

Post-PDC Phase Two:

1. This study will be a cross-sectional study, and therefore associations may be found, but we will be unable to assess causality.
2. For the Aim 4b comparing PDC participants and UNICEF sample, only similar age groups will be compared; therefore, the number of children may be reduced which might affect the power of the study and its external validity.
3. As this is a secondary dataset analysis, missing values are expected.
4. The gestational age and adjusted age are subject to misclassification due to recall bias.

Expanding-PDC Phase Three:

1. As this is primarily a secondary dataset analysis of routinely collected data, missing values are expected.

5. Ethical Considerations

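### Aim 4a compares baseline children assessed at 12-36 months with PDC children of no stated age range under five, by an unadjusted test; overlap between the two groups is also unchecked

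*Combined protocol and SAP*

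**What the plan says.** **Baseline group.** Section 3.1 describes children "aged between 12 to 36 months at the time of data collection". Section 3.6.2 repeats this for the Aim 4a comparator: "with medical, nutritional and developmental outcomes assessed at 12-36 months of age (the dataset from Aim 1". Section 3.4 limits them to discharges from October 2011 to October 2013.

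**PDC group.** Section 3.5.1 states: "Aim 4a will include only preterm and/or LBW (<2000g) infants for comparison with the baseline population of similar infants". Section 3.5.2 adds: "For Aim 4a, exclusion criteria will match the Baseline Phase One exclusion criteria listed above". Those exclusions concern consent, congenital heart disease, dysmorphology and asphyxia, not age. Section 3.5.3 draws household interviews from "patients who enrolled in the PDC at least 12 months prior to data collection". The only upper limit is the general one in Section 3.2: "All under 5 years of age, high risk (preterm, LBW) children enrolled in PDC since April, 2014 when PDC was initiated".

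**Age comparability.** Section 4 provides it for the other comparison: "For the Aim 4b comparing PDC participants and UNICEF sample, only similar age groups will be compared". No matching sentence exists for Aim 4a.

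**Analysis.** Section 3.6.4 compares the Aim 4a groups by chi-square or Fisher's exact test. If power allows, a logistic regression will look for predictors of delay, using backward selection among variables with bivariate p < 0.10.

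**Overlap.** Section 5.2 foresees that surveyed baseline children may later enter PDC where applicable. Section 3.6.3 appends PDC data to the de-identified comparison files and describes no check for a child who is in both.

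**The concern.** Aim 4a is the plan's comparison of PDC children with similar children who had no PDC support. If the share of children failing an ASQ domain, or the share undernourished, varies with age, then two groups with different age mixes will differ even when PDC does nothing. The specified test cannot separate the two explanations. The authors saw this need for Aim 4b but wrote no equivalent rule for Aim 4a.

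The secondary issue is membership. A child surveyed at baseline and later enrolled can contribute one record to each group, although the test treats the groups as independent. A baseline child who attended PDC before being surveyed would be worse placed, because that child would be counted as unexposed.

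**Working it through.** The plan gives no sample size, power, alpha or delay rate for Aim 4a, so there is no figure to reproduce. The checks below use the plan's own dates. Months since discharge stand in for age, and time from birth to discharge is ignored.

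**1. Formal age ranges.**
- Baseline: 12 to 36 months.
- PDC at household interview: about 12 months (enrolled at least 12 months) to under 60 months. The upper limit is carried over from the PDC population, of which the Aim 4a children are a subset.
- The word infants in Section 3.5.1 is not an age limit, because the baseline children aged 12-36 months are also called infants.
- Outcomes taken from records could come from younger children. Section 3.6.3 allows EMR data for Aim 4, and Appendix F starts clinic ASQs at 6 months.

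**2. Ages on the Section 6.2 Phase Two schedule, if assessment took place between August 2015 and May 2016.** PDC opened in April 2014.
- A child born at opening is 16 months old in August 2015 and 25 months in May 2016.
- A PDC child over 36 months must have been older than 36 − 16 = 20 months at opening (August 2015) or 36 − 25 = 11 months (May 2016).
- The PDC group could therefore be younger or older than baseline, and the mix can differ inside 12-36 months as well as above it. Restriction without adjustment is not enough.

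**3. What age imbalance could do (illustration only; every input is assumed).** Suppose there is no PDC effect, two-sided alpha is 0.05, and delay prevalence is 40% or 50% except in an age band found only in the PDC group, where it is 10-20 points higher. A share s of PDC children lies in that band.
- Spurious difference d = s × prevalence gap, from 0.25 × 0.10 = 0.025 to 0.50 × 0.20 = 0.10.
- Rejection rate = 1 − Φ((1.96·SE0 − d)/SE1) + Φ((−1.96·SE0 − d)/SE1), with SE0 the pooled and SE1 the unpooled standard error.
- With 60 to 200 per group this gives about 6% to 52%. With 120 per group it gives about 7% to 34%. The 120 is the number of participant incentives in the Phase One budget, not a stated sample size.

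**4. Can a baseline child also be a PDC child?** Months since discharge for the October 2011-October 2013 window:

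| Date | Range | Share of window at or below 36 months |
|---|---|---|
| April 2014 (opening) | 6-30 | 24/24 |
| August 2015 | 22-46 | 14/24 = 58% |
| May 2016 | 31-55 | 5/24 = 21% |
| October 2016 | 36-60 | none below 36 |

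On the Section 6.2 schedule the whole window is still under five, and a 12-36 month limit alone would not remove overlap. From about October 2016 it would. These are shares of calendar time, not counts of children.

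**5. Was the survey wholly before PDC?** A child discharged in October 2013 reaches 12 months in about October 2014, six months after opening. Either part of the survey followed the launch, or the later discharges in the window were not surveyed.

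**6. Effect of overlap on the test.** With equal groups, shared fraction f and within-child correlation r, Var(difference) = 2p(1−p)/n × (1 − f·r). Actual alpha = 2 × [1 − Φ(1.96/√(1 − f·r))]. Both f and r are assumed.
- f = 0.1: 4.8% (r = 0.2), 4.3% (r = 0.6).
- f = 0.4: 4.1% (r = 0.2), 2.5% (r = 0.6).

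Power = Φ((δ − 1.96)/√(1 − f·r)), with δ the standardised effect. At f = 0.4 and r = 0.6, √0.76 = 0.872, so:
- nominal 80% becomes Φ(0.842/0.872) = 83%;
- nominal 90% becomes Φ(1.282/0.872) = 93%;
- nominal 30% becomes Φ(−0.524/0.872) = 27%.

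Power falls only when nominal power is below 50%.

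**The case against.** The best defence is that the measures are already age-standardised. Each caregiver answers the ASQ form for the child's age (Section 3.6.1), and nutrition is judged by z-scores (Section 3.6.2). The enrolment rule sets an effective floor of 12 months at interview. On the Section 6.2 schedule most children enrolled as newborns would fall inside 12-36 months anyway, and Section 4 disclaims causality. This lowers the likely size of the problem. It does not close it, because the share failing a domain or stunted can still vary with age, and Section 4 itself warns: "The gestational age and adjusted age are subject to misclassification due to recall bias". A causality disclaimer does not make the age mixes comparable.

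It is also fair that the overlap matters less than the age issue. A child surveyed before PDC and again after it is correctly classified each time.

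A reader might infer more than the documents support:
- *That the age gap favours PDC.* Actual ages are not given, and the PDC group could be younger or older.
- *That there is no adjustment at all.* A logistic model is planned, but it is conditional, is a search for predictors, and need not retain age or PDC exposure.
- *That overlap inflates false positives or generally costs power.* With positive within-child correlation it does neither (step 6).
- *That the survey was safely before PDC, or that baseline is contaminated.* The summary and Section 5.2 suggest the survey came first, but step 5 shows this cannot hold for the whole discharge window unless later discharges were left out. Whether any child attended before the survey is not stated.
- *That many children are in both groups.* Section 5.2 allows later enrolment and gives no number.

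**Conclusion.** The point holds and should be fixed. As written, Aim 4a sets 12-36 months against a PDC range open to under 60 months, with no similar-age rule and an unadjusted main test. This conclusion rests on the text alone. The size and direction of any age bias are unknown, and the 6% to 52% range only shows what assumed imbalances would do.

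The membership gap is real but secondary. The documents allow a child to be in both groups and do not rule out PDC attendance before the survey, and no check is described for either. Overlap makes the independent-samples test conservative under the null, and its extent is not given. The shares of 58% falling to 21% apply only if assessment took place on the Section 6.2 Phase Two dates. The text available does not show which activity falls in which column. Section 2 marks Aim 4a as under way in a document approved in September 2017, so later assessment is possible.

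**What to change.** **Main change, for Aim 4a.**
- Include only PDC assessments made at 12-36 months, and restrict both groups to the ages they share.
- Make the main comparison a prespecified age-adjusted model or age-stratified analysis, with PDC exposure kept in regardless of its p-value.
- Add birth weight, gestational age and socioeconomic status if numbers allow.
- Report the chi-square or Fisher test as secondary.

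**Secondary change.** Where matching on the registry identifiers listed in Section 3.5.3 is permitted, count no child in both groups, exclude from baseline any child with a PDC visit before the survey, and report both numbers. If matching is not permitted, exclude PDC children from the October 2011-October 2013 discharge window as a sensitivity analysis only. That rule drops PDC children who were never surveyed. On the Section 6.2 schedule it also leaves neonatal-unit PDC children at most 22 (August 2015) to 31 (May 2016) months past discharge, so baseline would need the same upper age.

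**Cost.** The change needs eligibility and analysis wording plus one record match, on data already held or being collected. Age at data collection is already a Phase One variable. The price is a smaller PDC group and possible trimming of a baseline sample that Section 2 already calls small. Matching may also need permission, because Section 3.6.3 keeps the linking file for EMR quality checks and the comparison files are de-identified.
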